7.2.1. Primary Analysis

The primary efficacy endpoint is survival (based on all-cause mortality) at Day 29 and will be compared between the 2 treatment groups using a one-sided Mantel-Haenszel (MH) test of the difference in two proportions stratified by intubated or not intubated on Day 1 and a family-wise Type I error of 0.025. The estimated MH risk difference will be summarized along with the 2-sided 95% confidence interval (CI) using Mantel-Haenszel stratum weights ([Mantel, 1959](#)) and the Sato variance estimator. Handling of missing data for the primary analysis is described in [Section 7.2.1.1](#).

Survival will also be analyzed using the method of Kaplan and Meier (KM) and compared using a log-rank test stratified by intubated or not intubated on Day 1 as a sensitivity analysis. Hazard ratio and risk reduction will be summarized from a Cox proportional hazards model stratified by intubated or not intubated on Day 1. Confidence intervals (95%) will be presented for the survival estimate at Day 29 based on the complementary log-log transformation. Kaplan-Meier curves for both treatment groups will be produced.

A sensitivity analysis of the primary endpoint will also be performed using a 3-level categorical outcome of 3 (alive and discharged from the ICU); 2 (alive and in the ICU); or 1 (death). The 2 treatment groups will be compared using a proportional odds model with covariates for treatment group and the randomization stratification factor. If the assumption of proportional odds is rejected, a different approach will be considered.

Additional sensitivity analyses will include:

- A logistic regression with covariates for treatment group, age, sex, region, and randomization stratification factor. The estimate of the difference in survival proportions will be based on this logistic regression ([Ge, 2011](#)).

- A Cox proportional hazards model with covariates for treatment group, age, sex, region, and randomization stratification factor. The treatment group hazard ratio and risk reduction from the model will be summarized.

A summary table and listing of patients who died during the study will also be provided with reason for death, where available.

An interim analysis of the primary endpoint will also be conducted as described in [Section 7.4](#).

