7.2.1.2. Subgroup Analysis

A summary of survival at Day 29 will be produced by the following subgroups:

- Randomization stratification factor: intubated, not intubated
- Age group: <50 years, 50 to <70 years, ≥ 70 years
- Sex: Male, Female
- Region: United States, Europe, Asia
- Race: Asian, Black or African American, White, Other
- Ethnicity: Hispanic/Latino/Spanish origin, Not of Hispanic/Latino/Spanish origin
- Smoking status: Current/Former, Never
- Subgroups based on anticipated pre-existing conditions at baseline. Additional subgroups may be summarized depending on the distribution of medical histories of the patients in the study
 - Hypertension
 - Diabetes mellitus
 - Obesity
 - Respiratory conditions (eg asthma, COPD, pulmonary fibrosis/hypertension)
 - Coronary artery disease
- Subgroups based on anticipated concomitant medications used as BSC. Additional subgroups may be summarized depending on the distribution of medications used by patients during the study.
 - Use of any antivirals
 - Use of any immunomodulators
 - Use of any steroids
 - Use of any hydroxychloroquine/chloroquine
 - Use of any convalescent plasma

For each subgroup, the following descriptive summaries of survival will be produced:

- Summary of the number of patients
- Summary of the number (percentage) of patients with survival at Day 29
- Estimated risk difference between the 2 treatment groups along with a 95% CI
- Two-sided p-value from a stratified test of the difference in 2 proportions (if the sample size within a subgroup is too small, an unstratified test will be used)

- Hazard ratio and 95% CI from a Cox proportional hazards model with treatment covariate

If the use of concomitant medications is imbalanced by treatment group, the patients randomized to the ravulizumab + BSC group as a whole may be compared to subgroups of the BSC alone group with certain medication use (eg, antivirals, immunomodulators, hydrochloroquine/chloroquine).

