9.3. Sample Size, Power, and Randomization

A sample size of 243 patients (162 ravulizumab + BSC, 81 BSC alone) is required to ensure at least 90% power and detect an improvement in survival from 60% in the BSC alone group to 80% in the ravulizumab + BSC group at Day 29.

This sample size calculation was performed in EAST 6.5 and assumes:

- 1-sided Z-test of the difference in 2 proportions,
- Type I error = 0.025,
- Pooled variance,
- 2:1 randomization on the 2 treatment groups,
- One interim analysis at 50% information which will be after collecting primary efficacy data on approximately 122 patients. The early stopping boundaries for efficacy and futility (non-binding) will be constructed using α -spending function as Lan-DeMets spending function with O'Brien-Fleming flavor and β -spending function as Gamma(-4) ([Lan, 1983](#); [Hwang, 1990](#)).

Considering a nonevaluable rate of 10%, this study is planned to randomize approximately 270 patients (180 ravulizumab + BSC, 90 BSC alone).

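### Subgroup hazard ratios (SAP 7.2.1.2) are specified without the intubation stratum that the overall hazard ratio uses, so the two are not estimated on the same basis

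*SAP*

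**What the plan says.** Randomization is stratified by Day 1 intubation (Protocol 6.3). Protocol 9.4.1.1 leaves the detail of the subgroup analyses to the SAP.

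- **Overall HR (SAP 7.2.1).** "Hazard ratio and risk reduction will be summarized from a Cox proportional hazards model stratified by intubated or not intubated on Day 1". The code in SAP 9.5.2.1 has treatment as the only model term plus a separate strata statement for intubation.
- **Adjusted overall HR (SAP 7.2.1, sensitivity).** "A Cox proportional hazards model with covariates for treatment group, age, sex, region, and randomization stratification factor".
- **Other Cox models.** Those for Day 60/90 survival (7.2.2.6), dialysis (7.2.3.1) and clinical improvement (7.2.3.2) are all stratified by intubation.
- **Subgroup p-value (SAP 7.2.1.2).** "Two-sided p-value from a stratified test of the difference in 2 proportions", with the proviso that "if the sample size within a subgroup is too small, an unstratified test will be used".
- **Subgroup HR (SAP 7.2.1.2).** "Hazard ratio and 95% CI from a Cox proportional hazards model with treatment covariate". No stratum is named, and SAP 9.5.2 has no subgroup code.

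The subgroup section is introduced with "For each subgroup, the following descriptive summaries of survival will be produced". One of the subgroup factors is intubation itself: "Randomization stratification factor: intubated, not intubated".

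**The concern.** Subgroup HRs are usually read, often on a forest plot, against the overall HR. Here the overall estimate would condition on intubation and the subgroup estimates would not.

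Two things follow. First, a Cox HR that omits a prognostic factor is attenuated on average even when the arms are balanced on it, provided there is a treatment effect. Second, stratified randomization balances intubation overall, but not within subgroups of age, comorbidity or background medication. Chance imbalance there goes straight into an unstratified estimate, in either direction.

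At stake is how descriptive results are read: part of a difference between a subgroup HR and the overall HR could come from the model. The wording is also open enough for two programmers to produce different subgroup HRs from it.

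**Working it through.** **1. The plan's own figure.** The documents state no figure for the subgroup HRs. The sample size can be checked. SAP 9.3 sets out to "detect an improvement in survival from 60% in the BSC alone group to 80% in the ravulizumab + BSC group at Day 29" with one-sided alpha 0.025, 90% power, pooled variance and 2:1 allocation. The pooled survival proportion is (0.6 + 2×0.8)/3 = 0.7333.

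BSC patients = [1.960√(0.7333×0.2667×1.5) + 1.2816√(0.24 + 0.16/2)]² / 0.2² = (1.0615 + 0.7250)²/0.04 = 79.8, so 80 BSC and 240 in total.

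The plan's 243 (162:81) has 90.4% power as a fixed design, and 90.4% to 90.7% in simulation with the interim look. 243/0.9 = 270. The design assumptions reproduce.

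**2. Implied HR.** Under proportional hazards, ln(0.8)/ln(0.6) = 0.2231/0.5108 = 0.437. This is taken as the common HR within each stratum.

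**3. Assumptions.** The documents give neither the intubated share nor mortality by intubation status. I assume half intubated, 40% BSC mortality overall, exponential survival and censoring at Day 29 (SAP 9.5.1), and vary the mortality split.

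**4. Mechanism, by hand, at a 60%/20% split.** Day 29 survival on BSC is 0.40 intubated and 0.80 not. On ravulizumab it is 0.40^0.437 = 0.670 and 0.80^0.437 = 0.907. The intubated share of survivors is 0.40/1.20 = 33% on BSC and 0.670/1.577 = 42% on ravulizumab. The treated risk set keeps more high-risk patients, which moves the unstratified HR toward 1.

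**5. Large-sample size.** The treatment-only Cox estimate b solves ∫[w₁f₁(1−E) − w₀f₀E]dt = 0, with E = w₁S₁eᵇ/(w₁S₁eᵇ + w₀S₀), w₁ = 2/3 and w₀ = 1/3. S and f are the survival and density in each arm, averaged over the two strata.

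| BSC mortality, intubated / not | Treatment-only HR | Shift in log HR | Share of log HR kept |
|---|---|---|---|
| 40% / 40% | 0.437 | 0 | 100% |
| 50% / 30% | 0.443 | 0.014 | 98% |
| 60% / 20% | 0.463 | 0.058 | 93% |
| 70% / 10% | 0.499 | 0.133 | 84% |

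The stratified model targets 0.437 in every row. For a true HR of 0.70, the last three rows give 0.705, 0.722 and 0.751. For a true HR of 1, every row gives 1.000.

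Other intubated shares, at the same 40% overall: 70% intubated with 50%/16.7% gives 0.450; 30% intubated with 75%/25% gives 0.481.

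**6. Finite subgroups (3,000 simulations per setting, HR from mean log HR).**

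| Split | n | Unstratified / stratified HR | SE of log HR (unstratified) | Unstratified closer to 1 |
|---|---|---|---|---|
| 50/30 | 45 | 0.426 / 0.418 | 0.615 | 49% |
| 50/30 | 90 | 0.437 / 0.431 | 0.420 | 52% |
| 50/30 | 243 | 0.444 / 0.436 | 0.250 | 62% |
| 60/20 | 45 | 0.458 / 0.429 | 0.607 | 56% |
| 60/20 | 90 | 0.457 / 0.429 | 0.415 | 63% |
| 60/20 | 243 | 0.461 / 0.434 | 0.248 | 72% |

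At n = 90 and 60/20, the difference between the two log HRs has SD 0.168 around a mean of ln(0.457/0.429) = 0.063. In a single subgroup the direction is therefore uncertain.

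**7. Precision.** In a separate simulation at n = 135, the interval excludes 1 in 66.4% (unstratified) against 67.6% (stratified) of cases for 50/30, 63.5% against 69.9% for 60/20, and 58.1% against 72.7% for 70/10. At n = 60 and 60/20, the root mean squared error of the log HR is 0.552 for both models.

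**The case against.** **The omission is partly inferred.** The bullet does not say unstratified, and the stratified overall model also has treatment as its only covariate. This stands as far as it goes: a strata statement is unspecified, not ruled out. But the neighbouring p-value bullet and the SAP's other Cox models all state how intubation is handled, and there is no subgroup code to settle it, so clarification is still needed.

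**The effect is small for any one subgroup.** This stands. A reader might infer that most subgroup HRs will lie closer to 1 than the overall HR because of the model. Treating the overall HR as fixed at 0.437 and the SE as 0.42 (n = 90), the chance is Φ(0.014/0.42) = 51% for 50/30 and Φ(0.058/0.42) = 55% for 60/20, barely more than even.

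**The larger figures need favourable settings.** This stands. A subgroup of 135 is 135/243 = 56% of the evaluable sample, and many listed subgroups will be smaller. The only coverage loss seen (93.0% against 94.8%) is at 70/10. That is a wide contrast for a trial in which every patient needs mechanical ventilation and anyone intubated for more than 48 hours before Screening is excluded (Protocol 5.1 and 5.2).

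**A treatment-only HR is a legitimate marginal quantity.** True, and judging its coverage against the within-stratum HR presupposes the stratified target. It does not explain why the overall HR should be of one kind and the subgroup HRs of another.

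**Using the small-sample fallback mixes models in one display.** This stands, and the fix has to deal with it.

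**Conclusion.** The point holds as a minor inconsistency of specification. As written, the subgroup HR omits the stratum that the overall HR uses and that the subgroup p-value uses by default.

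With half the patients intubated and 40% BSC mortality overall, an HR of 0.437 becomes about 0.44 to 0.46 for splits of 50/30 to 60/20, and about 0.50 only at 70/10. These splits are assumptions. The attenuation is an average effect that needs both a treatment effect and a prognostic stratum. At n = 90 the shift of 0.014 to 0.058 in log HR is at most about a seventh of the standard error (0.058/0.42 = 0.14).

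A reader might go further and conclude that subgroup and overall HRs cannot be compared, that the subgroup intervals will miss a common effect, or that the trial's conclusion is exposed. The documents do not support any of these. The shift is small beside sampling error, and stratifying changes nothing in the intubated and not-intubated subgroups. The outputs are labelled descriptive and carry no alpha. The primary analysis is a stratified risk difference, and each subgroup also gets a risk difference to read against it.

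**What to change.** In SAP 7.2.1.2:

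1. Specify the subgroup HR and 95% CI from a Cox model with treatment as covariate, stratified by the randomization stratification factor, except within the intubated and not-intubated subgroups.
2. Apply the small-sample fallback already written for the p-value, and flag every subgroup where the unstratified HR is used.
3. Show an unstratified overall HR as the reference for the flagged subgroups.

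The cost is a few lines of SAP text, the strata statement already in the SAP 9.5.2.1 code, and one extra overall estimate. No new data are needed. The downside is small: expect little or no gain in precision in subgroups of about 60 or fewer, where the benefit is mainly a consistent basis for reading the results.

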7.2.1.3. Multicenter Studies

Since a small number of patients may be anticipated at certain sites, site will not be used in efficacy analyses; region will be used instead.

7.2.1.4. Hypothesis Testing and Significance Level

All hypothesis testing other than for the primary analysis will be 2-sided and performed at the 0.05 level of significance. All estimates of efficacy parameters will be accompanied by 2-sided 95% CIs.

7.2.1.5. Sensitivity and Supplementary Analyses

Sensitivity and supplementary analyses for the primary endpoint are described in [Section 7.2.1](#). Briefly these analyses include:

- Different missing data mechanisms to assess the impact of missing data
- Time to event analysis
- Categorical analysis
- Logistic regression model
- Cox proportion hazards model
- The primary analyses described for the ITT population will also be performed using the PPS

7.2.2. Secondary Analyses

A closed testing procedure will be applied to control the type I error for the analyses of the primary and secondary endpoints at Day 29. If the primary endpoint is statistically significant in favor of ravulizumab, the secondary endpoints will be evaluated according to the following rank order:

1. Number of days free of mechanical ventilation at Day 29,
2. Duration of ICU stay at Day 29,
3. Change from baseline in SOFA score at Day 29,
4. Change from baseline in SpO₂/FiO₂ at Day 29,
5. Duration of hospitalization at Day 29.

The hypothesis testing will proceed from highest rank (#1) the number of days free of mechanical ventilation at Day 29 to the lowest rank (#5) duration of hospitalization at Day 29, and if statistical significance is not achieved at an endpoint ($p \geq 0.05$), then endpoints of lower rank will not be considered to be statistically significant. Confidence intervals and p-values will be presented for all secondary efficacy endpoints for descriptive purposes, regardless of the outcome of the closed testing procedure.

An additional secondary endpoint will be assessed beyond Day 29 regardless of the results of the closed testing procedure: Survival (based on all-cause mortality) at Day 60 and Day 90.

The PPS will be used in a sensitivity analysis for all secondary efficacy endpoints.

7.2.2.1. Number of Days Free of Mechanical Ventilation at Day 29

The number of days free of mechanical ventilation at Day 29 will be summarized by treatment group for all patients and by mortality. The number of days free of mechanical ventilation at Day 29 will be compared between treatment groups using an analysis of covariance (ANCOVA), adjusting for age and the randomization stratification factor, among survivors (ie, the number of days alive and free of mechanical ventilation).

Missing data will be imputed using a multiple imputation approach assuming the data are MAR and using a regression model with covariates for treatment group, the randomization stratification factor, age, sex and presence of a pre-existing condition at baseline (diabetes mellitus, obesity, respiratory condition, and/or coronary artery disease). Sensitivity analyses will include:

- Worst-case scenario: missing days up to Day 29 for patients randomized to ravulizumab + BSC group will be considered as alive and not free of mechanical ventilation and missing days for patients randomized to BSC group will be considered as alive and free of mechanical ventilation for the remaining days up to Day 29
- All available data: no imputation of missing data
- Best-case scenario: missing days up to Day 29 for patients randomized to ravulizumab + BSC group will be considered as alive and free of mechanical ventilation and missing days for patients randomized to BSC group will be considered as alive and not free of mechanical ventilation for the remaining days up to Day 29
- Delta-adjustment tipping point analysis ([O’Kelly and Ratitch, 2014](#)): missing data for patients randomized to ravulizumab + BSC group are imputed by shifting the number of days alive and free for the observed patients downward by delta until any positive conclusion drawn from the primary analysis is reversed; refer to [Appendix 9.5.2.2.1](#) for additional details

7.2.2.2. Duration of ICU Stay at Day 29

The duration of ICU Stay at Day 29 will be summarized by treatment group for all patients and by mortality. Duration of ICU stay at Day 29 will be compared between the 2 treatment groups using an ANCOVA, adjusting for age and randomization stratification factor, among survivors (ie, the number of days alive and not in the ICU). Missing data will be handled as described for number of days free of mechanical ventilation at Day 29. The proportion of patients discharged

from the ICU will also be summarized and compared between the 2 treatment groups in a similar manner as the primary analysis of the primary endpoint.

7.2.2.3. Change from Baseline in SOFA Score at Day 29

Changes in SOFA score from Day 1 to Day 29 will be summarized by treatment group and study visit for all patients and by mortality.

Changes in SOFA score will be analyzed using a restricted maximum likelihood (REML)-based repeated measures approach (i.e. MMRM, [Mallinckrodt, 2008](#)) and all available longitudinal data. The model will include fixed effects for baseline SOFA score, age, randomization stratification factor, treatment group indicator, study day (Day 5, 10, 15, 22, 29), and study day by treatment group interaction. An unstructured covariance structure will be used to model the within patient errors. If this analysis fails to converge, the following structures will be tested and the final covariance structure will be determined by Akaike's information criterion (AIC): first-order autoregressive, compound symmetry, and Toeplitz. The Kenward-Roger approximation will be used to estimate denominator degrees of freedom. For patients who die, remaining values up to Day 29 will be imputed as a score of 24, the worst possible value.

A sensitivity analysis will be performed using a missing not at random (MNAR) mechanism for the missing data, where it will be assumed that unobserved outcomes for patients who discontinue early from the ravulizumab + BSC group will follow the trajectory of outcomes similar to the control group (BSC alone), taking into account observed values prior to discontinuation ([O'Kelly and Ratitch, 2014](#)). Patients discontinuing early from the BSC alone group will be assumed to have outcomes similar to the BSC alone patients who remain on their randomized treatment. Refer to [Appendix 9.5.2.2.2](#) for additional details.

7.2.2.4. Change from baseline in SpO₂/FiO₂ at Day 29

Changes in SpO₂/FiO₂ from Day 1 to Day 29 will be summarized daily by treatment group for all patients and by mortality.

Changes in SpO₂/FiO₂ will be also be analyzed using a REML-based repeated measures approach (i.e. MMRM, [Mallinckrodt, 2008](#)) and all available longitudinal data. The model will include fixed effects for baseline SpO₂/FiO₂, age, randomization stratification factor, treatment group indicator, study day (Day 5, 10, 15, 22, 29), and study day by treatment group interaction. An unstructured covariance structure will be used to model the within patient errors. If this analysis fails to converge, the following structures will be tested and the final covariance structure will be determined by Akaike's information criterion (AIC): first-order autoregressive, compound symmetry, and Toeplitz. The Kenward-Roger approximation will be used to estimate denominator degrees of freedom. The daily post-baseline SpO₂/FiO₂ scores will be mapped to study day as described in [Appendix 9.4.6](#). For patients who die, remaining values up to Day 29 will be imputed as a score of 0, the worst possible value.

A sensitivity analysis will be performed using a control-based MNAR mechanism for the missing data as described for change from baseline in SOFA score at Day 29.

This analysis will be repeated for changes in PaO₂/FiO₂, where available, as a sensitivity analysis.

7.2.2.5. Duration of Hospitalization at Day 29

Duration of hospitalization at Day 29 will be analyzed in a similar manner as duration of ICU stay (ie, the number of days alive and not hospitalized). Missing data will be handled as described for number of days free of mechanical ventilation at Day 29. The proportion of patients discharged from the hospital will also be summarized and compared between the 2 treatment groups in a similar manner as the primary analysis of the primary endpoint.

7.2.2.6. Survival at Day 60 and Day 90

Survival (based on all-cause mortality) at Day 60 and Day 90 will be estimated using the KM method and compared using a log-rank test stratified by intubated or not intubated on Day 1. Hazard ratio and risk reduction will be summarized from a Cox proportional hazards model stratified by intubated or not intubated on Day 1. Confidence intervals (95%) will be presented for the survival estimates at Day 60 and Day 90 based on the complementary log-log transformation. KM curves for both treatment groups will be produced.

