7.1.3.2. Disease Characteristics

The following disease characteristics will be summarized:

- Number (percentage) of patients with a positive SARS-CoV-2 test
- Number (percentage) of patients hospitalized
- Number of days from onset of signs and symptoms to hospitalization and to Day 1
- Number of days from hospitalization to Day 1
- Number (percentage) of patients in the ICU
- Number of days from first ICU date to Day 1
- Oxygen saturation level (SpO₂), PaO₂ from arterial blood gas, amount of supplemental oxygen (FiO₂) received, SpO₂/FiO₂ and PaO₂/FiO₂ at baseline
- Number (percentage) of patients on respiratory support and method of support on Day 1
- SOFA score at baseline
- Number (percentage) patients by smoking status

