9.5.2.2. SAS Code for the Secondary/Exploratory Efficacy Endpoints

9.5.2.2.1. Analysis of Covariance (ANCOVA)

For some secondary endpoints, an ANCOVA model will be used to compare the 2 treatment groups. The basic SAS code for this analysis is given by:

```
proc glm data = adef;  
class trt01p intub;  
model aval = trt01p age intub / solution;
```

```
lsmeans trt01p / cl diff stderr;  
run;
```

where aval is the number of days.

Missing data will be imputed using a multiple imputation approach assuming the data are MAR and using a regression model. The basic SAS code for this is:

```
Proc mi data=adeff out=outmi seed=1306528 nimpute=pctmissing round=. . . . 1 maximum=. . .  
.. 29 minimum=. . . . 1;  
class trt01p intub sex comorbid;  
var trt01p intub sex age comorbid aval;  
monotone reg(aval = trt01p intub sex age comorbid / details);  
run;
```

If an imputed value for a patient is less than the observed number of days until dropout, then the observed number will be used. The imputed data sets will then be analyzed by imputation using the ANCOVA method described above and the PROC MIANALYZE procedure will be used to generate valid statistical inferences about these parameters. The basic SAS code for this is:

```
Proc mianalyze data=parameterestimates;  
modeffects estimate;  
stderr stderr;  
run;
```

A sensitivity analysis will use a delta-adjustment tipping point approach where the missing data for patients randomized to ravulizumab + BSC group are imputed by shifting the number of days for the observed patients downward by delta. For each value of delta, the treatment effect will be determined, and the value of delta for which the nominal 2-sided p-value crosses 0.05 will be considered as the ‘tipping point’ in the sense that the positive conclusion drawn from the primary analysis is reversed. The basic SAS code for this is:

```
Proc mi data=adeff out=outmi seed=1306528 nimpute=pctmissing round=. . . . 1 maximum=. . .  
.. 29 minimum=. . . . 1;  
class trt01p intub sex comorbid;  
var trt01p intub sex age comorbid aval;  
monotone reg(aval = trt01p intub sex age comorbid / details);  
mmar adjust (aval / shift=delta adjustobs=(trt01p='Ravulizumab + BSC'));  
run;
```

where delta is the shift parameter for the imputed values of days for patients randomized to ravulizumab + BSC group.

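### The ANCOVAs for ventilator-free, ICU-free and hospital-free days omit baseline severity that the trial already collects: a missed gain in precision, not an error of validity

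*SAP*

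**What the plan says.** SAP 7.2.2.1 compares ventilator-free days, rank 1 of the testing sequence, "using an analysis of covariance (ANCOVA), adjusting for age and the randomization stratification factor", among survivors. SAP 4.1 explains that this means days alive and free of ventilation, so death is folded into the count. SAP 7.2.2.2 does the same for ICU-free days (rank 2), "using an ANCOVA, adjusting for age and randomization stratification factor, among survivors (ie, the number of days alive and not in the ICU". For rank 5, SAP 7.2.2.5 says: "Duration of hospitalization at Day 29 will be analyzed in a similar manner as duration of ICU stay".

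The code in SAP 9.5.2.2.1 agrees with the text: "model aval = trt01p age intub / solution". The regression that imputes missing day counts has no severity term either: "monotone reg(aval = trt01p intub sex age comorbid / details".

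Baseline severity is available. SAP 7.1.3.2 lists "SOFA score at baseline" and "SpO₂/FiO₂ and PaO₂/FiO₂ at baseline" among the characteristics to be summarised, and the schedule in Protocol 1.3 marks SOFA at both Screening and Day 1. The SAP already uses baseline SOFA as a covariate for change in SOFA (7.2.2.3) and baseline SpO2/FiO2 for change in SpO2/FiO2 (7.2.2.4).

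No sensitivity analysis of the day counts adds either variable, and no reason for leaving them out is given. The adjustment for further important baseline covariates in Protocol 9.4.1.1 concerns the primary endpoint only. SAP 7.2.1 carries it out with age, sex, region and stratum.

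**The concern.** Severity at entry is an obvious candidate predictor of days on the ventilator, in the ICU and in hospital. Intubation is a single yes/no split in a population in which every eligible patient already needs mechanical ventilation (Protocol 5.1, criterion 4). SOFA runs from 0 to 24 over six organ systems, and SAP 5.1.2.4 itself describes multiple organ failure as a marker of mortality in the ICU. Because death counts against the patient in these endpoints, a predictor of death should help to predict them.

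Precision matters here for two reasons. The sample size was set for survival alone, with 81 evaluable controls, and no power is stated for any day count. Ventilator-free days also stands first among the secondary endpoints, so a miss there prevents every lower rank from being declared significant. Adjusting for a prognostic baseline value reduces residual variance and corrects chance imbalance in severity without adding patients.

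**Working it through.** **1. The plan's own figure.** The only powered endpoint is survival: 60% against 80%, one-sided 0.025, 90% power, 2:1 (SAP 9.3). The pooled proportion is (0.6 + 2 × 0.8)/3 = 0.733. Controls needed = [1.960 × √(0.733 × 0.267 × 1.5) + 1.282 × √(0.24 + 0.16/2)]² / 0.2² ≈ 79.8, so 80 controls and 240 in total, against 243 stated. Power at 162:81 is 90.4% with a fixed sample and 90.3% with the interim look. 243/0.9 = 270 randomized, as stated. The design reproduces, and nothing below alters it.

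**2. Inputs for the day counts.** The SAP gives two-sided 0.05 (7.2.1.4) and 2:1 allocation. It gives no SD, effect size, power or correlation with baseline severity. Two assumptions are therefore needed:
- 80% power under the planned ANCOVA, as a reference point;
- a partial R², the share of variance left after treatment, age and intubation that the added baselines explain.

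**3. Formula.** The planned model has four parameters (intercept, treatment, age, intubation). Adding SOFA and SpO2/FiO2 makes six. The standard error is multiplied by

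f = √[(1 − R²) × (N − 4)/(N − 6)].

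The equivalent sample size is N/f². With 80% power as the base, power is Φ[(1.960 + 0.842)/f − 1.960].

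**4. Results for N = 243**, where (N − 4)/(N − 6) = 239/237 = 1.0084:

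| Partial R² | f | Equivalent N | Power |
|---|---|---|---|
| 0 | 1.004 | 241 | 79.7% |
| 0.05 | 0.979 | 254 | 81.7% |
| 0.10 | 0.953 | 268 | 83.7% |
| 0.20 | 0.898 | 301 | 87.7% |

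For example, at R² = 0.10, f = √(0.90 × 1.0084) = 0.953. A partial R² of 0.05 to 0.20 corresponds to a partial correlation of about 0.22 to 0.45 (the square roots).

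**5. Does N matter?** Hardly. At 270 randomized the factors for 0.05, 0.10 and 0.20 are 0.978, 0.952 and 0.898. With 178 patients, the expected number of survivors (162 × 0.8 + 81 × 0.6 = 178.2), they are 0.980, 0.954 and 0.900.

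**6. SOFA alone.** With one added covariate the worst case is √(239/238) = 1.002, a standard error 0.2% larger.

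**7. Illustration.** A small simulation under invented assumptions (243 patients, severity correlated with intubation, a 0 to 29 day score that includes death) gave changes in standard error from 0.4% larger to about 9% smaller as the prognostic strength of severity rose from nil to strong.

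**The case against.** **Nothing is wrong with the planned model.** It is prespecified, consistent between text and code, and adjusts for the stratification factor and age. This stands. A reader might infer that leaving out severity biases the results for ranks 1, 2 and 5. The documents do not support that: with death counted in the score as SAP 4.1 describes, the comparison is protected by randomization with or without further covariates.

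**The gain is assumed.** This also stands. What counts is the correlation after age and intubation. Requiring ventilation at entry narrows the range of severity, and the upper SOFA respiratory scores require respiratory support, so SOFA overlaps with intubation. A reader might take a partial correlation of 0.3 to 0.5 and claim the equivalent of 10% to 33% more patients (1/(1 − r²) − 1). Nothing in the documents supports that as the expected range; at 0.2 the same formula gives 4%. Under 2:1 allocation an ANCOVA without interactions does not guarantee a gain if slopes differ by arm.

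**Availability.** A reader might infer that both baselines are measured in every patient at Screening and Day 1. For SOFA the schedule shows this. For oxygenation, the text available here shows no visit marks in that row, and footnote 9 of the schedule asks for a predose Day 1 value only in ravulizumab-treated patients. It is also unsupported that few baselines will be missing: SOFA needs six components, and its printed creatinine bands leave 401 to 440 μmol/L unscored.

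**The SAP baseline is not clean.** SAP 9.4.2 accepts any value up to and including Day 1. SAP 4.2 (item 1) lets Day 1 assessments in undosed patients fall on the calendar day after randomization. Footnote 9 records the day's best oxygenation reading, which could follow the infusion. In an open-label trial such a covariate could be affected by treatment or knowledge of it. This stands, but it governs how the change is written and does not defeat it.

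**The two covariates overlap.** SpO2/FiO2 is the surrogate for the SOFA respiratory component, so their gains do not add up. This is why SOFA comes first and SpO2/FiO2 is optional.

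**Conclusion.** The point holds as a missed efficiency. Three of the five endpoints in the secondary sequence, including the first, are analysed without a severity measure that the trial collects and that the SAP already accepts as a covariate elsewhere. The downside of adding it is about 0.4% on the standard error with both covariates. The upside is about 2% to 10% off the standard error, or about 2 to 8 points of power. That range rests on an assumed partial R² of 0.05 to 0.20 and an assumed 80% base, neither of which can be checked from the documents. The omission is certain; the size of the benefit is not. The primary endpoint, its sample size and its stopping boundaries are unaffected. The change is worth making, but the trial's validity does not depend on it.

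**What to change.** Before comparative data by treatment group are seen:

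- Add baseline SOFA as a continuous covariate to the ANCOVAs of SAP 7.2.2.1, 7.2.2.2 and 7.2.2.5. Baseline SpO2/FiO2 may be added too, with a note that it overlaps with the SOFA respiratory component.
- Add the same terms to the matching multiple-imputation model and update the code in SAP 9.5.2.2.1, including the tipping-point version. Missingness at random is also easier to defend when the imputation model contains severity.
- For these covariates, use the last value before randomization or, failing that, before the first infusion.
- State a simple rule for missing baselines that ignores treatment group, such as the overall mean. Treat a post-randomization value in a BSC-alone patient as missing.
- List the change in SAP 4.1, because Protocol 9.4.1.2 names the present covariates. SAP 4.1 already gives the SAP precedence.

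The cost is a few SAP sentences and code lines, plus one or two degrees of freedom. No new data collection is needed for SOFA, which the schedule already places at Screening.
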